5.0 Study Design and Statistical Analysis Plan

- 5.1 *Describe the basic study design/approach (e.g., qualitative study using five focus groups of first year students to describe assimilation into the university community; randomized controlled trial of a behavioral change intervention to increase dietary intake of whole grains; pre- post-test evaluation of new pedagogical techniques to improve adult literacy):*

This will be a quantitative study examining variables indexing physiology, mobility, and subjective experience of participants as they are exposed to stimuli designed to move them through stages of the defense cascade.

- 5.2 *Describe corresponding data analysis plan/approach (e.g., content analysis of focus group transcripts; descriptive analysis followed by linear regression modeling; nonparametric analysis of pre- and post-test measures):*

Data will be analyzed using Pearson's correlations to examine degree of correspondence between primary variables of interest that index mobility, SNS, and PNS activation, as well as SUDS. Additionally, as time allows, moderation analysis will be conducted to determine if higher scores on trauma, PTSD, dissociation, anxiety, and BIITS phobia affect the overall patterns observed in the primary variables of interest.

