1.0 Study Summary

Study Title	Defense Cascade: Physiology, Mobility, and Subjective Experience
Study Design	In-lab virtual reality (VR) stimuli will be presented for this psychophysiology study with online prescreen. Data will be analyzed using correlational analyses and OLS regression measuring mobility, SNS activation, PNS activation, and SUDS ratings. Moderation will be tested based on scores on anxiety, trauma, dissociation, and interoceptive awareness.
Primary Objective	Complete Master's thesis requirements for [name] investigating whether patterns of mobility map to physiological patterns and subjective experience when engaged in the defense cascade.
Secondary Objective(s)	I plan to submit a paper for publication in psychology peer-reviewed research journal as well as to use the data for poster presentations at conferences such as the Society for Psychophysiological Research.
Study Population	Young adults
Sample Size	200 for online prescreen, 100 to be invited to lab
Research Intervention(s)/ Investigational Agent(s)	Research intervention/stimulus will be a series of videos and experiences all presented in a VR environment, with peripheral audio and tactile enhancement. Investigational agents will include surveys, collection of psychophysiological measures including ECG, ICG, EDA, and accelerometry, behavioral observations from participant video footage, and post-hoc interviews with participants.
Study Duration for Individual Participants	1.5 hours for online prescreen, 2 hours for in lab; total of 3.5 hours
Acronyms and Definitions	
VT: Virginia Tech VR: Virtual Reality MBL: Mind-Body Lab ECG: ElectroCardioGram ICG: Impedance CardioGraphy EDA: ElectroDermal Activity PEP: Pre-Ejection Period HF-HRV: High-Frequency Heart Rate Variability PTSD: PostTraumatic Stress Disorder ANS: Autonomic Nervous System SNS: Sympathetic Nervous System PNS: Parasympathetic Nervous system SUDS: Subjective Units of Distress Scale

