2.0 Objectives

2.1 *Describe the purpose, specific aims, or objectives of this study:*

The objectives of this study are to map patterns of mobility to patterns of physiology and self-reported subjective experience during a perceived threat experience.

2.2 *State the hypotheses to be tested:*

Mobility will be moderately positively correlated with SNS activation and moderately negatively correlated with PNS activation.

Transitions in mobility will be supported by ANS coactivation.

SNS activation will be moderately positively correlated with SUDS scores.

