4.0 Study Endpoints

*4.1 Describe the primary and secondary **study** endpoints. See links below for discussion of study endpoints and how they may differ from study*

objectives. These are most common in clinical trials but are sometimes applicable to other types of biomedical research, as well as social, behavioral, or educational research. See link below for a discussion.

https://docs.google.com/document/d/1Wocz7K7a0hCQJPP0_khh5l1SQQjhGDDGHzcOPRHR5Tw/edit?usp=sharing

Primary endpoint will be the Pearson's correlations between the following variables:

- Mobility in X, Y, and Z planes each with pre-ejection period (PEP)
- Mobility in X, Y, and Z planes each with phasic electrodermal activity (EDA)

Secondary endpoint will be the Pearson's correlations between the following variables:

- Mobility in X, Y, and Z planes each with HF-HRV
- PEP and Subjective Unites of Distress Scale (SUDS)
- EDA and SUDS
- HF-HRV and PEP during one minute intervals where mobility is transitioning

- 4.2 *Describe any primary or secondary **safety** endpoints. These should be included for all studies that are greater than minimal risk. (Minimal risk: The probability and magnitude of harm or discomfort anticipated in the research that are not greater in and of themselves than those ordinarily encountered in daily life or during the performance of routine physical or psychological examinations or tests.):*

In order to minimize dangers associated with disoriented movement in the VR environment, one research assistant will be assigned the role of participant spotter, attending to any unsafe movements that participants may attempt while navigating their virtual environment.

Experiencing VR can increase the risk of dizziness or nausea because of the discrepancy between the actual and the virtual environment. The consent form includes a description of this possibility and how the participant can address it if they do not have tolerance of such symptoms.

The probability of psychological discomfort is assessed to be the same or less than that of watching a horror movie or playing a horror video game.

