7.0 Study Intervention(s)/Investigational Agent(s)

7.1 *Describe the study interventions (including behavioral interventions) and/or investigational agents (e.g., drugs or devices) to be used in this study. Consider each of the items listed below:*

- *Drug/Device Handling: If the research involves drugs or devices, describe your plans to store, handle, and administer the drugs or devices so that they will be used only on subjects, and only by authorized investigators.*
- *Describe whether any of the following will be used: microwaves, X-rays, DEXA scans, general anesthesia, or sedation*

- *If control of the drugs or devices used in this protocol will be accomplished by following an established, approved organizational SOP (e.g., Research Pharmacy SOP for the Control of Investigational Drugs, etc.), please reference the SOP in this section.*

This study's intervention will be a series of video clips projected in a VR environment, combined with a threat scenario designed uniquely for the VR environment. Additional interventions will include an audio white noise stimulus, a tactile vibrational stimulus, and a post-stimulus debrief. Video clips will be viewed as if on a projector within the VR environment and will include: (1) an approximately 3-minute instructional video on the use of the SUDS rating system, (2) an approximately 4-minute non-narrated video depicting marine life in a sunny, non-threatening situation accompanied by a soothing musical score, and (3) a portion of the threat scenario begins with images projected on the virtual projector. Both (1) and (2) are vanilla baseline clips, designed to measure physiological and mobility responses in a non-threatening situation as a baseline. The unique VR scenario begins again by a presentation of stimuli as if projected on a movie screen within the VR environment. The culmination of this threat scenario depicts a creature emerging from the projected movie screen and appearing to approach the participant in the VR environment.

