Participants will be assisted in placing the VR headset on and ensuring that they are adjusted for comfort and focus. Physiological recording will then begin while participants are shown the 3-minute instructional video in the use of the SUDS rating system. Participants will then be asked to report their first SUDS rating shown as if on a projector screen within the VR environment. Participants will be instructed that as they watch the subsequent videos, they will be periodically prompted for their SUDS ratings. They will further be instructed to complete this as quickly as possible. This timeliness instruction is designed to minimize distraction from the stimulus. SUDS requests will be given at one-minute intervals throughout the remainder of the experiment.

Following the SUDS instructional video, participants will see a 10 second black screen on the virtual projector within the VR environment, followed by the marine video as described in section 7.0. Following the marine video, participants will again see a 10 second black screen on the virtual projector within the VR environment. While the projected screen continues to be blank, a 98 decibel burst of white noise will be delivered with 0 ms rise time and 750 ms duration (Vila et al., 2007). This stimulus will be used to measure cardiac defensive response to acoustic stimuli in isolation of new visual stimuli. There will continue to be no new visual stimuli for the subsequent 80 seconds to allow a complete cardiac defensive response to be captured without other sensory confounds.

Finally, the VR experience will begin with the imagery described in section 7.0. As the creature described in section 7.0 appears to approach the participant and reach for them, the tactile module will be engaged to deliver a mild, but sudden vibration to the neck of the participant. This

will serve as the equivalent of a jump scare (a sudden cinematic stimulus meant to surprise), but with a switch in sensory modality.

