14.0 Number of Subjects

14.1 *Indicate the total number of subjects to be enrolled and how this number was determined (e.g., sample size calculation [show], number of available subjects in a finite pool, number of tests funding award would allow):*

This study will seek to enroll 85 participants. A power analysis was calculated using the G*Power applet (Faul et al., 2007) to determine required sample size for a target correlation of 0.3. With $\alpha = 0.05$ and $\beta = 0.20$, the target effect size requires a sample size of at least 85 participants. It is estimated that 85 out of the 100 participants completing online screening will be in compliance with abstention requirements

14.2 If this is a multi-site study, indicate the number of subjects to be enrolled at this site and the total to be enrolled from all sites:

N/A

14.3 If applicable, indicate the number of potential subjects you expect to screen for enrollment, and the number of subjects you will need to complete the research procedures:

It is estimated that 200 subjects will be screened for enrollment in order to obtain 100 subjects to invite to the lab. Of these, we need 85 participants to follow abstention requirements and complete the research procedure.

14.4 If the study has more than one procedure, indicate the total number of subjects to undergo each procedure separately:

N/A

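### Plain Pearson correlations sized as 85 independent pairs do not match repeated recordings within each person, and the unit of analysis is never stated

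*Protocol*

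**What the plan says.** The objective in section 2.1 is to "map patterns of mobility to patterns of physiology and self-reported subjective experience during a perceived threat experience". Section 2.2 predicts correlations of mobility with sympathetic and parasympathetic activation, and of sympathetic activation with SUDS. It also predicts that transitions in mobility are accompanied by autonomic coactivation.

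Section 4.1 sets the endpoints: "Primary endpoint will be the Pearson's correlations between the following variables". Six primary pairs follow: mobility in each of three planes with PEP, and with phasic EDA. The secondary endpoints are Pearson correlations too, including HF-HRV with PEP, restricted to one-minute intervals in which mobility is changing.

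Section 5.2 repeats the method: "Data will be analyzed using Pearson's correlations to examine degree of correspondence between primary variables of interest". It adds only moderation analyses if time allows. The study summary in section 1.0 is slightly wider: "Data will be analyzed using correlational analyses and OLS regression measuring mobility, SNS activation, PNS activation, and SUDS ratings".

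On data collection, section 8.1 starts physiological recording at the instructional video and says "SUDS requests will be given at one-minute intervals throughout the remainder of the experiment". Section 7.1 describes the instructional and marine clips as "designed to measure physiological and mobility responses in a non-threatening situation as a baseline". Section 14.1 reports a power calculation "to determine required sample size for a target correlation of 0.3" with alpha 0.05 and beta 0.20, giving 85 participants.

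**The concern.** Each participant supplies a series, not a single pair of values, and the series is designed to run from calm to threat. A simple Pearson test, like the OLS regression named in the summary, treats its rows as independent and does not separate two different associations. One is whether a person's autonomic state moves with that person's mobility. The other is whether people who move more on average also differ in autonomic level.

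The protocol does not say which rows enter the correlation. If minutes are pooled over people, the p-value is too small and r is a blend of the two associations. If each person is averaged, the p-value is sound, but changes during the threat are averaged away. A positive pooled result could be a clustering artefact, and a null person-mean result could hide real coupling within people. All six primary correlations are exposed to this, and so are the secondary ones.

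**Working it through.** **1. Reproduce the plan's figure.** Inputs from 14.1: r = 0.3, alpha 0.05 (taken as two-sided), power 0.80. By Fisher z:

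n = ((1.960 + 0.842) / atanh(0.3))² + 3 = (2.8016 / 0.3095)² + 3 = 84.93, so 85.

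The arithmetic is right for one correlation from 85 independent pairs, that is, one pair per person.

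**2. Assumptions for what follows.** The documents give no intraclass correlations (ICCs) and no length for the threat scenario. I take k = 10 one-minute epochs. The stated parts before the threat alone last about 180 + 10 + 240 + 10 + 80 = 520 seconds, or 8.7 minutes. I vary k and the ICCs, written as ICC of one variable / ICC of the other.

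**3. Rows pooled, no true association.** With a, b the two ICCs, the variance of r is inflated by D = 1 + (k − 1)ab, and the true two-sided error is 2[1 − Φ(1.96/√D)].

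| k | ICCs | D | Rows | Effective rows | Type I error |
|---|---|---|---|---|---|
| 10 | 0.3/0.3 | 1.81 | 850 | 470 | 14.5% |
| 10 | 0.5/0.5 | 3.25 | 850 | 262 | 27.7% |
| 10 | 0.5/0.7 | 4.15 | 850 | 205 | 33.6% |
| 10 | 0.7/0.7 | 5.41 | 850 | 157 | 39.9% |
| 4 | 0.5/0.5 | 1.75 | 340 | 194 | 13.8% |
| 15 | 0.5/0.5 | 4.50 | 1275 | 283 | 35.6% |

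Simulation agrees: about 15%, 28% and 34% to 35% for the first three rows.

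**4. One mean per person.** With within-person r = w and between-person r = β, the expected correlation of person means is

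[β√(ab) + w√((1−a)(1−b))/k] / √{[a + (1−a)/k][b + (1−b)/k]}.

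Take w = 0.30, a = 0.5, b = 0.7, k = 10. The numerator is 0.5916β + 0.0116 and the denominator is √(0.55 × 0.73) = 0.6336. The chance of significance uses atanh(r)·√82 against 1.96.

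| β | Person-mean r | Chance of p < 0.05 | Pooled r |
|---|---|---|---|
| 0 | 0.018 | 5% | 0.116 |
| 0.1 | 0.112 | 17% | 0.175 |
| 0.2 | 0.205 | 47% | 0.235 |
| 0.3 | 0.298 | 80% | 0.294 |

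The pooled value is 0.5916β + 0.3873w. The within-person association is 0.30 in every row, so the person-mean result is driven almost wholly by β. In simulation, a correlation of person-centred values recovered 0.30 in every scenario run.

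**5. Is a standard repeated-measures correlation enough?** It removes person means but assumes independent residuals. I simulated the null with 85 people, 10 epochs and first-order autoregressive errors in both variables. Its 5% test rejected about 6% to 7% of the time at a lag-1 correlation of 0.3, 10% to 11% at 0.5 and 16% to 17% at 0.7. Serial correlation therefore has to be modelled.

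**The case against.** The strongest reply is that the protocol never says it will pool minutes. One-minute timing is explicit only for SUDS and for the HF-HRV/PEP transition endpoint. The six primary pairs have no stated epoch. The mobility and SUDS hypotheses do not say within or between persons, and the person-level moderators and the sample size fit a person-level reading. All of this stands. A reader might infer that the primary analysis does treat minute rows as independent, or that the study asks no between-person question. The text supports neither.

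Nor are pooling and averaging the only options. Correlating each person's baseline-to-threat change, or computing r within each person and combining the results, would avoid the pooling error. The protocol excludes neither, but describes neither. The 5% figure for person means is also a worst case that needs a between-person r of zero.

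It can further be said that epoch length and data reduction belong in a separate SAP. For those details alone, that is fair. But section 5.0 is itself headed as the statistical analysis plan, and 4.1 makes the Pearson coefficient the endpoint. The choice of method is therefore fixed here, and it does not fit the transition hypothesis or the recording design.

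**Conclusion.** The concern holds in this form. The protocol fixes simple Pearson correlations, sizes them as 85 independent pairs and leaves the unit of analysis open, while its design yields repeated measures aimed at patterns during a threat. The figure of 85 is itself correct for a single person-level r of 0.3.

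The consequence depends on how the rows are formed. Under pooling, the false-positive rate is about 15% to 35% with 10 epochs and ICCs from 0.3/0.3 to 0.5/0.7, and 40% if both ICCs are 0.7. Under person means, the test is valid but can detect a within-person r of 0.30 only so far as people also differ between themselves in the same direction. These sizes rest on assumed ICCs and epoch counts, and the calculations in steps 3 and 4 leave out serial correlation.

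It would go too far to say that no reading of the plan gives a valid test. The defect is that none of the sound routes to the stated objective is specified.

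**What to change.** - **Sections 4.1 and 5.2:** state the epoch and the unit of analysis. Make the primary analysis a mixed model of each autonomic index on person-mean-centred mobility, with a participant random effect and serially correlated residuals.
- **SUDS and transition endpoints:** handle them likewise, with the relevant predictor centred within person.
- **Baseline:** use the recorded baseline period, as change from baseline or as an adjustment. Section 7.1 names both clips as baseline, so use both or state which.
- **Headline within-person r:** if one is wanted, take its interval and p-value from the mixed model or from a bootstrap that resamples participants, not from the standard repeated-measures correlation test.
- **Person-level Pearson correlations:** report them separately, as a description of differences between people.
- **Section 14.1:** state that 85 was sized for a single person-level r of 0.3.
- **Section 1.0:** align the reference to OLS with the revised method.

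The cost is protocol wording and slightly more analysis work. No new data or participants are needed.

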6.0 Setting

6.1 *Describe the sites or locations where your research team will conduct the research. Consider each of the items listed below:*

- *Identify where your research team will identify and recruit potential subjects.*
- *Identify where the team will perform the research procedures.*
- *Describe the composition and involvement of any community advisory board(s).*
- *For research conducted in other locations, describe:*
 - *Site-specific regulations or customs affecting the research at those locations.*
 - *Local scientific and ethical review structure at those locations. Examples include work in other cultures or ethnic groups (within or outside of the U.S.) and work with churches. The HRPP will provide additional guidance for international research.*

Undergraduates over 18 years old will be recruited as study participants via flyers posted in Williams Hall and via the Virginia Tech Psychology Department's participant management system, Sona.

Those signing up for the study will be directed to fill in an online prescreen. Those passing the prescreen will be invited to the in-lab portion of the study. This in-lab portion will be conducted in a room in Williams Hall. The room will contain physiological measuring equipment, a desktop computer, two small webcams, and a VR headset connected to the desktop computer.

There is no community advisory board for this study (only my department-specific Master's Thesis Committee). All research will be conducted at Williams Hall on the Virginia Tech Blacksburg campus.

7.0 Study Intervention(s)/Investigational Agent(s)

7.1 *Describe the study interventions (including behavioral interventions) and/or investigational agents (e.g., drugs or devices) to be used in this study. Consider each of the items listed below:*

- *Drug/Device Handling: If the research involves drugs or devices, describe your plans to store, handle, and administer the drugs or devices so that they will be used only on subjects, and only by authorized investigators.*
- *Describe whether any of the following will be used: microwaves, X-rays, DEXA scans, general anesthesia, or sedation*

- *If control of the drugs or devices used in this protocol will be accomplished by following an established, approved organizational SOP (e.g., Research Pharmacy SOP for the Control of Investigational Drugs, etc.), please reference the SOP in this section.*

This study's intervention will be a series of video clips projected in a VR environment, combined with a threat scenario designed uniquely for the VR environment. Additional interventions will include an audio white noise stimulus, a tactile vibrational stimulus, and a post-stimulus debrief. Video clips will be viewed as if on a projector within the VR environment and will include: (1) an approximately 3-minute instructional video on the use of the SUDS rating system, (2) an approximately 4-minute non-narrated video depicting marine life in a sunny, non-threatening situation accompanied by a soothing musical score, and (3) a portion of the threat scenario begins with images projected on the virtual projector. Both (1) and (2) are vanilla baseline clips, designed to measure physiological and mobility responses in a non-threatening situation as a baseline. The unique VR scenario begins again by a presentation of stimuli as if projected on a movie screen within the VR environment. The culmination of this threat scenario depicts a creature emerging from the projected movie screen and appearing to approach the participant in the VR environment.

Following presentation of the VR stimuli, participants will be assisted in removing the VR headset, will be asked to complete the MAIA questionnaire, and then will be asked to review a split-screen video showing the video they just watched in part of the screen and the video footage of themselves watching the stimulus videos in the other part of the screen. During this period, participants will be asked to comment on or explain any of the physiological, mobility, or subjective experiences they remembered during the stimulus video. This period will actually continue to track their physiology and mobility in hopes of better understanding the mechanisms by which physiology and mobility recover following the experience of a threat.

7.2 *List the name of all drugs (including any vitamins, supplements, herbs, or nicotine) to be used in the study. Indicate whether they have FDA approval, and list any limitations for their use:*

N/A

7.3 *List all devices, how they will be used, their purpose in the study, and if they will be used in a manner consistent with their approved uses. If they will be used in ways that are not yet FDA approved, indicate whether they*

need an IDE or a determination that they are exempt from the IDE Determination. If a determination of significant risk or non-significant risk is needed for any of the devices, include the researcher's recommendation for each of those devices:

Biopac physiological equipment will be used in accordance with its specified uses, as follows:

The BioNomadix Non-Invasive Cardiac Output system will be used to gather ICG data, which provides one of two inputs to the calculation of PEP, an estimate of SNS control of the heart. The Biopac ECG100C and Biopac RSP100C and/or the BioNomadix RSP & ECG System will be used to gather respiration and ECG data, which provides the second of two inputs to the calculation of PEP. It is also used to calculate HF-HRV, an estimate of PNS control of the heart. The Biopac Tri-axial Accelerometer and/or the BioHarness Physiology Monitoring System and/or the BioNomadix Accelerometer System will be used to calculate participant mobility in X, Y, and Z planes. Finally, the Biopac EDA100C and/or the BioNomadix PPG & EDA System will be used as a second estimate of SNS activation using galvanic skin response, an SNS index not influenced by the cardiac system. Uncertainty about which units will be used (the "and/or" language above) are due to uncertainty at the time of this application about whether the BioNomadix units will be funded by pending applications for scholarship and lab funds. Nevertheless, all aforementioned units will be used in accordance with their approved and attended purposes.

Two Microsoft webcams will be used to collect video footage of the participants from two angles: one will record facial expressions, while the other will record from the participant's side for behavioral coding to assess degree to which the participant is exhibiting approach versus avoidance behavior.

A noise-cancelling wireless headset will be used to deliver the audio portion of the video clips and to deliver a 98 decibel burst of white noise with 0 ms rise time and 750 ms duration.

A vibrational unit will be used to deliver a 5 volt vibration to the neck of the participant. This voltage is roughly three times the intensity of the vibration delivered by a standard smart phone in "vibrate" mode.

An Oculus Quest or Oculus Go headset will be used to present the Virtual Reality portion of the experiment to participants.

7.4 If the drug is investigational (has an IND) or the device has an IDE or a claim of abbreviated IDE (non-significant risk device), include the following information:

- Identify the holder of the IND/IDE/abbreviated IDE.
- Explain procedures followed to comply with sponsor requirements for FDA regulated research for the following:

FDA Regulation	Applicable to:		
	IND Studies	IDE studies	Abbreviated IDE studies
21 CFR 11	X	X	
21 CFR 54	X	X	
21 CFR 210	X		
21 CFR 211	X		
21 CFR 312	X		
21 CFR 812		X	X
21 CFR 820		X	

N/A

